3.3.5. Imputation of Incomplete Dates

An incomplete date is any date for which either the day, month, or year is unknown, but all three fields are not unknown. An incomplete date occurs when the exact date an event occurred or ended cannot be obtained from a subject. For many of the analyses, a complete date is necessary in order to determine if the event should be included in the analysis (i.e., if the event is treatment-emergent) or to establish the duration of an event. In such cases, incomplete dates will be imputed.

For purposes of imputation, all events with an incomplete end date are assumed to have ended on or before the day the form was completed. In an effort to minimize bias, the project statistician will impute dates in a systematic but reasonable manner, as described below.

For event start dates, if the month/year is the same as the Day 1 month/year then the date will be set to the date of Day 1. In other cases, missing days will be imputed as the day component of Day 1; missing months/years will be imputed as the month/year of Day 1.

For event end dates, if the month/year is the same as the event start date month/year then the date will be set to the date of the event start date. In other cases, missing days will be imputed as the day component of the event start date; missing months/years will be imputed as the month/year of the event start date.

3.3.6. Presentations by Study Visit

Nominal Study Visits as obtained from the CRF or applicable laboratory results will be utilized for summary displays. If assessments are collected multiple times within a given Study Visit, the result closest to the scheduled visit date will be used for summary presentations. If two measurements have the same distance to the expected date, the earlier value will be used. If a scheduled assessment and an unscheduled or ET assessment are collected within a given visit, the value from the scheduled assessment will be chosen over the value from the unscheduled assessment. ET visits will be windowed to the Week 18 visit. Unscheduled visits will be windowed based on study day, according to the table below. All assessments will be presented in the listings.

Study Day	Windowed Study Visit
11 - 17	Week 2
39 - 45	Week 6
67 - 73	Week 10
95 - 101	Week 14
123 - 129	Week 18

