7.9 LIVER ADVERSE EVENTS

The algorithm (Chalasani and Regev 2016) described in Table 8 will be used to monitor for drug-induced liver injury (DILI).

Table 8. Algorithm to Monitor for DILI

| Treatment Emergent ALT | Treatment Emergent Total Bilirubin (TB) | Liver Symptoms | Actions |
|--|--|----------------|---|
| Normal Baseline: ALT >2x ULN | Normal | None | Repeat ALT, AST, ALP, TB, in 2-5 days after receipt of the scheduled ALT results (Table 1). |
| Elevated Baseline: ALT >2x Baseline or >300 U/L (whichever occurs first) | Patients with Gilbert's syndrome: No change in Baseline TB | None | Follow up for symptoms. |

| Treatment Emergent ALT | Treatment Emergent Total Bilirubin (TB) | Liver Symptoms | Actions |
|---|--|---|---|
| Normal Baseline: ALT >5x ULN | Normal | None | Interrupt study drug. Initiate close monitoring and workup for competing etiologies. |
| Elevated Baseline: ALT >5x Baseline or >500 U/L (whichever occurs first) | Patients with Gilbert's syndrome: No change in Baseline TB | | Study drug can be restarted only if another etiology is identified and liver enzymes return to baseline. |
| Normal Baseline: ALT >2x ULN | TB >2x ULN | None | Interrupt study drug. Initiate close monitoring and workup for competing |
| Elevated Baseline: ALT >2x Baseline or >300 U/L (whichever occurs first) | Patients with Gilbert's syndrome: Doubling of direct bilirubin | | etiologies. Study drug can be restarted only if another etiology is identified and liver enzymes return to baseline. |
| Normal Baseline: ALT >2x ULN | Normal or elevated | Severe fatigue, nausea, vomiting, right upper quadrant pain | Interrupt study drug. Initiate close monitoring and workup for competing |
| Elevated Baseline: ALT >2x baseline or >300 U/L (whichever occurs first) | - | | etiologies. • Study drug can be restarted only if another etiology is identified and liver enzymes return to baseline. |

Note: Baseline is the average of the Screening and Baseline visit ALT measurements.

As described in Table 8, close monitoring of the subject must be initiated if certain signals of a possible DILI are detected. At a minimum, close monitoring includes:

- Repeating liver enzyme and serum bilirubin tests 2-3 times weekly. The frequency of retesting can decrease to once a week or less if abnormalities stabilize or if the study drug has been discontinued and the subject is asymptomatic.
- Obtaining a more detailed history of the subject's symptoms and prior or concurrent diseases.

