3.3.7. Definitions and Terminology

Age

The age of a subject is defined as the number of whole years between the subject's birth date and the treatment start date.

Day 0 (Baseline)

Day 0 is the earliest day that study drug is initiated.

Study Day

Study Day is defined relative to Baseline (Day 0). Thus, the study day of an event is calculated as:
$$\text{Study Day} = \text{event date} - \text{date of Day 0}.$$

Study Visit

Study Visit is the nominal visit as recorded on the CRF.

Days on Treatment

Days on Treatment is calculated as Final Day on Treatment based on the End of Study eCRF page – First Day on Study Treatment + 1.

Baseline Value

For purposes of analysis, the baseline value is defined as the last non-missing value obtained prior to initiation of study drug.

Change from Baseline

Change from baseline for a given endpoint is defined as the Study Day X value minus the Baseline Value.

Percent (Relative) Change from Baseline

Percent, or relative, change from Baseline for a given endpoint is defined as the change from Baseline at Study Day X divided by the Baseline value, multiplied by 100 $((\text{CFB}/\text{BASE}) \times 100)$.

Adverse Event

An AE is defined as any untoward medical occurrence associated with the use of a drug in humans, whether or not considered drug related. An AE can be any unfavorable and unintended sign (including an abnormal laboratory finding), symptom, or disease (new or exacerbated) temporally associated with the use of the investigational product, regardless of whether it is considered to be related to the investigational product. All AEs will be recorded on the Adverse Event CRF.

Treatment-emergent Adverse Event

A TEAE will be an AE that occurred during the study after the first dose of study drug or that was present prior to dosing and exacerbates after the first dose of study drug. Additionally, it is assumed that an Adverse Event which was reported to have started on Day 1 without an associated onset time occurred after the initiation of study drug.

Concomitant Medications

Concomitant medications are those medications taken on or after the initiation of study drug. This definition includes medications started prior to the initiation of study drug, but continuing concomitantly with study drug.

Prior Medications

Prior medications are those medications taken prior to the initiation of study drug.

Total Bile Acid

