5.3.2. Clinical Laboratory Assessments, Vital Signs, Height, and Weight

Descriptive summaries of selected (quantitative) clinical laboratory results, and change from Baseline will be presented by time point and treatment group. Laboratory abnormalities will also be summarized by treatment group. Shift tables (low, normal, high) for change from Baseline to Week 18, or last available study visit, will be presented for all appropriate clinical laboratory parameters. Additionally, shift tables (normal, abnormal) for change from Baseline to Week 18, or last available study visit, will be presented for the clinical laboratory parameters listed below. Laboratory abnormalities will be determined using the following criteria:

Laboratory Parameter	Clinically Significant Abnormal Criteria
ALP	> 348 U/L
ALT	> 123 U/L
AST	> 102 U/L
Direct Bilirubin	> 0.20 mg/dL
Total Bilirubin	> 2.00 mg/dL

GGT	> 156 U/L in Males > 114 U/L in Females
Glucose	< 60 mg/dL
INR	≥ 1.3
HbA1c	≥ 9.5%

Additionally, descriptive summaries and change from Baseline in weight will be presented by timepoint and treatment group.

Values for all safety variables will be listed by subject and visit (as applicable).

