- 14.3.1.4 Treatment-Emergent Serious Adverse Events by System Organ Class and Preferred Term – Safety Set
- 14.3.1.5 Treatment-Emergent Adverse Events Leading to the Discontinuation of Study by System Organ Class and Preferred Term – Safety Set
- 14.3.4.1 Clinical Laboratory Chemistry Parameters by Time Point – Safety Set
- 14.3.4.2 Clinical Laboratory Hematology Parameters by Time Point – Safety Set
- 14.3.4.3 Clinical Laboratory Urinalysis Parameters by Time Point – Safety Set
- 14.3.4.4 Clinical Laboratory Abnormalities – Safety Set
- 14.3.4.5 Clinical Laboratory Parameter Shifts from Baseline to Week 18 – Safety Set
- 14.3.4.6 Clinical Laboratory Parameter Shifts to Abnormal from Baseline to Week 18 – Safety Set
- 14.3.5.1 Vital Signs by Study Visit – Safety Set
- 14.3.5.2 12-Lead ECG Assessments by Study Visit – Safety Set

Summary Figures

Efficacy

- 14.2.1.3 Bar Plot of Mean Absolute Change from Baseline at Week 18 in LFC
- 14.2.1.4 Bar Plot of Mean Percent Change from Baseline at Week 18 in LFC
- 14.2.1.5 Bar Plot of Proportion of Subjects with $\geq 30\%$ Reduction in LFC from Baseline to Week 18
- 14.2.1.6 Bar Plot of Proportion of Subjects who normalize LFC to $< 5\%$ at Week 18
- 14.2.1.7 Bar Plot of Proportion of Subjects who achieve $\geq 5\%$ absolute reduction in LFC from Baseline to Week 18
- 14.2.3.1 Bar Plot of Mean Change from Baseline by Time Point in Fasting Glucose
- 14.2.3.2 Bar Plot of Mean Change from Baseline by Time Point in HbA1c
- 14.2.3.3 Bar Plot of Mean Change from Baseline by Time Point in HOMA-IR
- 14.2.3.4 Bar Plot of Mean Change from Baseline by Time Point in AST
- 14.2.3.5 Bar Plot of Mean Change from Baseline by Time Point in ALT
- 14.2.3.6 Bar Plot of Proportion of Subjects who Normalize ALT at Week 18
- 14.2.3.7 Bar Plot of Mean Change from Baseline by Time Point in Lipids
- 14.2.3.8 Bar Plot of Mean Change from Baseline by Time Point in Pro-C3
- 14.2.3.9 Bar Plot of Mean Change from Baseline by Time Point in ELF
- 14.2.3.10 Bar Plot of Mean Change from Baseline by Time Point in Total Bile Acids
- 14.2.3.11 Bar Plot of Mean Change from Baseline by Time Point in C4
- 14.2.3.12 Bar Plot of Mean Change from Baseline by Time Point in FGF19

Data Listings

- 16.2.1.1 Subject Disposition
- 16.2.1.2 Informed Consent

- 16.2.2.1 Protocol Deviations/Violations
- 16.2.2.2 Inclusion/Exclusion Criteria
- 16.2.3 Reasons for Exclusion from Analysis Sets
- 16.2.4.1 Demographics
- 16.2.4.2 Medical History

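### Both laboratory shift tables use the last visit and by-visit summaries set aside unscheduled liver tests, so a liver peak that resolves can appear as no shift, and no worst-value liver table is specified

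*SAP*

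**What the plan says.** **Extra liver tests.** Protocol Section 7.9, Table 8, calls for a repeat test 2 to 5 days after the scheduled ALT result is received when the first threshold is crossed. The rows that interrupt study drug also start close monitoring, which includes "Repeating liver enzyme and serum bilirubin tests 2-3 times weekly". Restart requires that another cause is found and that enzymes are back at baseline.

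**By-visit summaries.** SAP Section 3.3.6 uses nominal visits for summary displays. For tests between visits, "Unscheduled visits will be windowed based on study day, according to the table below", and that table has five windows: days 11-17, 39-45, 67-73, 95-101 and 123-129. Where a visit has both kinds of result, "the value from the scheduled assessment will be chosen over the value from the unscheduled assessment". In addition, "ET visits will be windowed to the Week 18 visit", and "All assessments will be presented in the listings".

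**Shift tables.** SAP Section 5.3.2 states: "Shift tables (low, normal, high) for change from Baseline to Week 18, or last available study visit, will be presented". The normal/abnormal shift table uses the same time point and fixed cut-offs, for example ALT above 123 U/L and total bilirubin above 2.00 mg/dL. It is listed in SAP Section 10 as Table 14.3.4.6, "Clinical Laboratory Parameter Shifts to Abnormal from Baseline to Week 18". Protocol Section 9.2.5 has the same last-visit rule.

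**Other outputs.** SAP Section 5.3.2 also promises a summary of laboratory abnormalities by arm (Table 14.3.4.4), with no time point and no rule on unscheduled values. SAP Section 5.3.1 promises a summary of liver-specific adverse events by arm, but the table list in Section 10 has no such table.

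**The concern.** In a trial of a liver disease, the main laboratory safety question is how high ALT, AST and bilirubin went on treatment, in how many subjects per arm, and whether ALT and bilirubin rose together. The protocol orders extra tests at the times when a peak is most likely to be caught. The SAP then gives those tests the lowest priority in by-visit summaries and reads the shift tables at the end of treatment, when a transient peak may be over. Where this operates, the error runs towards showing no liver signal. At stake is the comparison of liver safety between the two doses and placebo. The efficacy analysis is not affected.

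**Working it through.** **1. Reproduce the windows.** Scheduled visits are on days 14, 42, 70, 98 and 126, each ±3 days (schedule of events in both documents). SAP Section 3.3.7 defines study day as event date minus the date of Day 0. So 14 ± 3 = 11-17, 42 ± 3 = 39-45, 70 ± 3 = 67-73, 98 ± 3 = 95-101 and 126 ± 3 = 123-129. These match the SAP table.

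**2. Where a Table 8 repeat falls.** Day of repeat = nominal day + o + t + r, where o is the visit's deviation (-3 to +3), t the laboratory turnaround and r the delay after receipt (2 to 5 days). The documents give no turnaround, so t = 0 to 5 is an assumption. The repeat misses its visit's window when o + t + r > 3. It cannot reach the next window: the latest case is 3 + 5 + 5 = 13 days after the nominal day, and the next window opens at least 25 days after it (39 - 14). Each t gives 5 visits × 7 deviations × 4 delays = 140 combinations.

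| t (days) | Outside every window | In window, displaced by scheduled value |
|---|---|---|
| 0 | 70 (50%) | 70 |
| 1 | 90 (64%) | 50 |
| 2 | 110 (79%) | 30 |
| 3 | 125 (89%) | 15 |
| 4 | 135 (96%) | 5 |
| 5 | 140 (100%) | 0 |

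The two columns always sum to 140. After a visit attended in its window with a valid result, every repeat stays out of the by-visit summary, whatever the turnaround. The percentages count combinations and are not probabilities.

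**3. Close monitoring, an illustration.** Tests every 3 days from day 49 to day 97 number (97 - 49)/3 + 1 = 17. Four fall in a window (days 67, 70, 73 and 97) and 13 in none. The four are used only if the Week 10 or Week 14 scheduled result is missing.

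**4. A resolved peak in the shift tables.** Take a subject with normal Baseline ALT who passes 5 × ULN, a Table 8 interruption criterion. If ULN is 41 U/L (assumed, 123/3), that is 205 U/L, above the SAP cut-off of 123. The same ordering holds for any ULN above 123/5 = 24.6 U/L. If ALT is normal again at Week 18 or ET, both shift tables read normal to normal. A shift to the worst value would read normal to high and normal to abnormal.

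**5. Subjects already above the cut-off.** Take ALT of 150 U/L at Screening and Baseline, rising to 450. This passes 2 × 150 = 300 but neither 5 × 150 = 750 nor 500, so with normal bilirubin and no symptoms only the repeat-test row of Table 8 applies. Both values exceed 123, so Table 14.3.4.6 shows abnormal to abnormal, even with the worst value. A Baseline of 150 is eligible (ALT below 5 × ULN) if ULN exceeds 150/5 = 30 U/L. This shows only that a fixed cut-off cannot register a rise from a raised Baseline.

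**6. Planned outputs.** SAP Section 10 lists no table of worst post-baseline values as such, none by Table 8 criterion, and none that pairs ALT with bilirubin.

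**The case against.** Several points on the other side are sound.

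- Liver enzymes and bilirubin are drawn at all five post-baseline visits, and Table 8 times its repeat from a scheduled result. The trigger value is therefore often scheduled. It stays in that visit's summary of values and changes, where SAP Section 5 includes the maximum.
- Preferring the scheduled value in a by-visit display is reasonable, since it avoids giving extra weight to subjects tested more often. The no-shift result comes from the last-visit rule in SAP Section 5.3.2, not from the selection rule alone.
- A subject who stops drug permanently should have an ET visit, which counts as Week 18, so ALT still raised then can show.
- Listings hold every value, adverse events may include abnormal laboratory findings, discontinuations for adverse events have their own table, and a DSMB reviews safety. Table 14.3.4.4 may count peaks: its title names no time point, and nothing says that the Section 3.3.6 rule governs it.

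These points narrow the gap but do not close it. A visit maximum does not give each subject's peak over the study, and listings give no comparison by arm. The documents do not require that meeting a Table 8 row be recorded as an adverse event.

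A reader might infer more than the documents support:

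- **That the peak is absent from the report.** The outputs above show otherwise.
- **That recovery by Week 18 is the usual course.** No source is given, and restart also requires that another cause be identified.
- **That the unmapped days measure the loss.** The windows cover 35 of days 1-129, leaving 94 (73%), but these are calendar days, not tests or subjects. Likewise, one subject in an arm of 39 is 2.6%, with no event rate behind it.
- **That the rise from 150 to 450 U/L illustrates a hidden interruption.** It meets only the repeat-test row.

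**Conclusion.** The point holds in a limited form. If the SAP is followed exactly, a transient ALT, AST or bilirubin peak that resolves before Week 18 or ET can appear as no shift. The Table 8 repeat and close-monitoring tests enter by-visit summaries only when they fall in a window that has no scheduled value. For repeats after an attended in-window visit with a result, the exclusion is complete under every turnaround from 0 to 5 days (assumed). A subject with raised Baseline ALT can also show no shift despite a large rise, because the categories are fixed.

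The number of subjects affected cannot be estimated from the documents. The data are collected and listed, and some peaks will be visible elsewhere. What is missing is a specified comparison by arm of each subject's worst liver values, against Baseline and with ALT and bilirubin together. That is worth correcting, but it does not mean that the plan discards the safety signal.

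**What to change.** In SAP Section 5.3.2, with matching entries in Section 10:

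1. Add shift tables from Baseline to the worst post-baseline value, including unscheduled and ET results, at least for ALT, AST, ALP and bilirubin. Keep the last-visit shifts. State how long after the last dose a value still counts; 30 days would match the minimum adverse event follow-up in Protocol Section 6.3.5.
2. State that Table 14.3.4.4 counts any post-baseline value, including unscheduled tests, and is exempt from the selection rule in SAP Section 3.3.6.
3. Tabulate by arm the subjects who meet each laboratory criterion of Protocol Table 8, and cross-tabulate peak ALT (as multiples of ULN and of Baseline) against peak total bilirubin. Say which Baseline applies: the note to Table 8 averages the Screening and Baseline ALT values, while SAP Section 3.3.7 takes the last value before dosing.

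The cost is a few sentences of SAP text and a few table programs on data already collected. No clinical rule changes. The downside is that subjects tested more often have more chances of an extreme value; the retained scheduled-visit tables put that in context.

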3.3.7. Definitions and Terminology

Age

The age of a subject is defined as the number of whole years between the subject's birth date and the treatment start date.

Day 0 (Baseline)

Day 0 is the earliest day that study drug is initiated.

Study Day

Study Day is defined relative to Baseline (Day 0). Thus, the study day of an event is calculated as:
$$\text{Study Day} = \text{event date} - \text{date of Day 0}.$$

Study Visit

Study Visit is the nominal visit as recorded on the CRF.

Days on Treatment

Days on Treatment is calculated as Final Day on Treatment based on the End of Study eCRF page – First Day on Study Treatment + 1.

Baseline Value

For purposes of analysis, the baseline value is defined as the last non-missing value obtained prior to initiation of study drug.

Change from Baseline

Change from baseline for a given endpoint is defined as the Study Day X value minus the Baseline Value.

Percent (Relative) Change from Baseline

Percent, or relative, change from Baseline for a given endpoint is defined as the change from Baseline at Study Day X divided by the Baseline value, multiplied by 100 $((\text{CFB}/\text{BASE}) \times 100)$.

Adverse Event

An AE is defined as any untoward medical occurrence associated with the use of a drug in humans, whether or not considered drug related. An AE can be any unfavorable and unintended sign (including an abnormal laboratory finding), symptom, or disease (new or exacerbated) temporally associated with the use of the investigational product, regardless of whether it is considered to be related to the investigational product. All AEs will be recorded on the Adverse Event CRF.

Treatment-emergent Adverse Event

A TEAE will be an AE that occurred during the study after the first dose of study drug or that was present prior to dosing and exacerbates after the first dose of study drug. Additionally, it is assumed that an Adverse Event which was reported to have started on Day 1 without an associated onset time occurred after the initiation of study drug.

Concomitant Medications

Concomitant medications are those medications taken on or after the initiation of study drug. This definition includes medications started prior to the initiation of study drug, but continuing concomitantly with study drug.

Prior Medications

Prior medications are those medications taken prior to the initiation of study drug.

Total Bile Acid

Total bile acid is calculated as the sum of all bile acid measurements and metabolites at a visit for a given subject.

Total Primary Bile Acid

Total primary bile acid is calculated as the sum of cholic acid, chenodeoxycholic acid, glycocholic acid, glycochenodeoxycholic acid, taurocholic acid, and taurochenodeoxycholic acid at a visit for a given subject.

Total Secondary Bile Acid

Total secondary bile acid is calculated as the sum of deoxycholic acid, lithocholic acid, glycodeoxycholic acid, glycolithocholic acid, taurodeoxycholic acid, and tauroolithocholic acid at a visit for a given subject.

Total Ursodeoxycholic Acid

Total ursodeoxycholic acid is calculated as the sum of ursodeoxycholic acid, glyoursodeoxycholic acid, and tauroolithocholic acid at a visit for a given subject.

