| Height | 6.3.2 | X | | | | | | | | |
| ECG | 6.3.3 | X | Xa | | X | | X | X | X | |
| Laboratory Assessments | | | | | | | | | | |
| Serum chemistry panel ^c | 6.2.2, 6.3.4 | X | X | X | X | X | X | X | X | |
| Lipid panel ^c | 6.2.2, 6.3.4 | X | X | | | X | | X | X | |
| Hematology with differential ^c | 6.3.4 | X | X | | | X | | X | X | |
| Coagulation panel ^c | 6.3.4 | X | X | | | X | | X | X | |

Clinical Protocol

| | Protocol | | | | Double-Blin | d Treatment | | | | |
|-----------------------------------|--------------------|-----------|-----------------------|------|-------------|-------------|-------|-------|----|-----------|
| | Section(s) | SCR | Baseline | WK 2 | WK 6 | WK 10 | WK 14 | WK 18 | ET | Follow-up |
| Visit Day | | -28 to -1 | 0 | 14 | 42 | 70 | 98 | 126 | | +30d |
| Procedure / Window | - | - | - | ±3d | ±3d | ±3d | ±3d | ±3d | - | +7d |
| HbA1c | 6.2.2 | У | ζ ^d | | | X | | X | X | |
| HOMA-IR | 6.2.2 | | X | | | | | X | X | |
| HIV and Hepatitis B/C | 6.3.4 | X | | | | | | | | |
| G6PD | 6.3.4 | X | | | | | | | | |
| Pregnancy test ^e | 6.3.4 | X | X ^{a,e} | | | | | X | X | |
| FSH test ^e | 6.3.4 | X | | | | | | | | |
| Urine drug test | 6.3.4 | X | | | | | | | | |
| Imaging and Biomarker Assessmen | its | | | | | | | | | |
| MRI-PDFF | 6.2.1 | У | ζ^{d} | | | | | X | X | |
| Corrected T1 and T2* | 6.2.1 | У | ζ^{d} | | | | | | | |
| Pro-C3 | 6.2.2 | | X | | | | | X | X | |
| ELF test | 6.2.2 | | X | | | | | X | X | |
| Bile acid panel ^c | 6.2.2 | | X | | | X | | X | X | |
| Safety Assessments | | | | | | | | | | |
| Adverse event monitoring | 6.3.5, 7.0 | X | Xa | X | X | X | X | X | X | X |
| Prior and concomitant medications | 4.5, 4.6, 6.3.6 | X | Xª | X | X | X | X | X | X | X |

^a Continued study eligibility confirmed based on updated medical history, targeted physical examination, vital signs, weight, ECG, negative urine pregnancy test (for FOCP), updated prior and concomitant medications, and any adverse events that have occurred since signing informed consent.

ET = Early Termination; SCR = Screening

^b Targeted physical examination of body systems or organs performed on symptom-driven basis (e.g., adverse events or other findings).

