5.0 EXPERIMENTAL PROCEDURES

5.1 PROCEDURES, MEASUREMENTS, AND EVALUATIONS

Study procedures are summarized across all scheduled study visits as indicated in the Study Design (Figure 1) and the Schedule of Time and Events (Table 1). Unscheduled visits may also occur at any time if medically warranted. Study related assessments performed at all visits will be recorded in the eCRF.

Throughout the study, clinical laboratory (blood and urine) samples will be collected during a fasting state (i.e., at least 8 hours prior to sample collection) and sent to the designated central laboratory for analysis. Study drug should be taken with water and food (e.g., meal or snack).

For subjects who cannot be contacted for either a return for a scheduled clinic visit or for follow-up assessments as described in this section, and who may be considered "lost to follow-up," at least 3 documented attempts should be made to establish contact with and to instruct the subject on how to complete study procedures. In the final attempt to contact the subject, a letter should be sent by certified mail to the subject's last known address.

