5.2.2. Primary Efficacy Analysis

LFC values and change from Baseline will be presented by treatment group and study visit. LS means, standard error, and corresponding 95% confidence intervals for absolute change from Baseline in LFC will be presented by treatment group, and LS mean differences between treatment groups will also be presented with their respective standard errors and confidence intervals. Differences in absolute change from Baseline in LFC will be assessed by analysis of covariance that includes treatment group as a fixed effect, and Baseline LFC and Baseline ALT as covariates. Comparisons of each active treatment group to placebo will be tested at the 5% level of significance without adjustment for multiple tests.

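### The Baseline rule leaves a second fasting, central-laboratory value unused for seven secondary analytes; adding it as a covariate is a cheap gain in precision

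*SAP*

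**What the plan says.** SAP 3.3.7 defines Baseline once for all endpoints: "For purposes of analysis, the baseline value is defined as the last non-missing value obtained prior to initiation of study drug".

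The schedules in Protocol Table 1 and SAP 1.2 place the serum chemistry panel (including ALT, AST, GGT and fasting glucose) and the lipid panel at both Screening and Day 0. Protocol 5.1 says that "clinical laboratory (blood and urine) samples will be collected during a fasting state" and are "sent to the designated central laboratory for analysis". Protocol 5.1.1 confines Screening to the 28 days before Day 0, and 5.1.2 places the Day 0 draw before dosing. Each of the seven analytes therefore has two untreated values, of which the analysis uses the later.

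SAP 5.2.5 analyses the laboratory endpoints by ANCOVA on treatment group and Baseline value. GGT is an endpoint in SAP 5.2.4 and has its own table, but is not named in the ANCOVA list. I assume that it is analysed in the same way.

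Baseline ALT has two further uses. The primary liver-fat model (SAP 5.2.2) has "treatment group as a fixed effect, and Baseline LFC and Baseline ALT as covariates", and SAP 5.2.5 selects subjects with elevated Baseline ALT for the normalisation endpoint. In Protocol 7.9 the liver-injury algorithm carries its own definition: "Note: Baseline is the average of the Screening and Baseline visit ALT measurements".

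**The concern.** These analytes vary from day to day within a person. A single reading is a noisier measure of a subject's usual level than two readings, so it explains less of the Week 18 variance and leaves a wider standard error on the treatment comparison. The second reading is already paid for, and neither document gives a reason for leaving it out.

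The trial is sized on liver fat alone, with 35 evaluable subjects per arm. Glucose metabolism, lipids and liver enzymes are named secondary objectives with no power calculation of their own, so precision that costs nothing to collect is worth having.

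The point does not extend to the other endpoints. HbA1c and MRI-PDFF have one pre-dose value, from Screening. HOMA-IR, Pro-C3, ELF and the bile acid panel are scheduled before dosing only at Day 0.

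**Working it through.** **The plan's own figure.** With a difference of 5, an SD of 6.3 and two-sided 5%, a two-sample t test has 89.7% power at 34 per arm and 90.5% at 35. Then 35/0.9 = 38.9, rounded up to 39, and 3 × 39 = 117. The figure reproduces. It concerns liver fat and does not depend on this point.

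**Formulae.** Take standardised values, with correlations rb (Screening with Day 0), r1 (Day 0 with Week 18) and r2 (Screening with Week 18). The ANCOVA residual variance is:

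- Day 0 only: 1 − r1²
- mean of the two: 1 − (r1 + r2)² / [2(1 + rb)]
- both as covariates: 1 − (r1² + r2² − 2·rb·r1·r2) / (1 − rb²)

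With Day 0 in the model, analysing the change or the Week 18 value gives the same treatment effect, so Day 0 can stay as the reference for change. The algebra covers absolute change, not percent change. The documents give none of these correlations, so all the values below are assumptions.

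**Equal correlations (rb = r1 = r2 = r).** The two ways of using both values coincide, and the ratio to Day 0 only is (1 + 2r)/(1 + r)².

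| r | Day 0 only | Both values | Ratio | Cut in SE | 35 per arm performs like |
|---|---|---|---|---|---|
| 0.5 | 0.750 | 0.667 | 0.889 | 5.7% | 39 |
| 0.6 | 0.640 | 0.550 | 0.859 | 7.3% | 41 |
| 0.7 | 0.510 | 0.424 | 0.830 | 8.9% | 42 |
| 0.8 | 0.360 | 0.289 | 0.802 | 10.4% | 44 |

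**Variance components (log scale).** Residual variance is sw² + sd² + sb²(1 − R), with R = sb²/(sb² + sw²/k) for k readings. The assumed SDs are sb 0.4 to 0.5 between subjects, sw 0.15 to 0.30 within subject, and sd 0 to 0.3 for true individual change.

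- Smallest gain (sb 0.4, sw 0.15, sd 0.3): 0.1322 falls to 0.1230, ratio 0.930, a 7% cut.
- Largest gain (sb 0.5, sw 0.15, sd 0): 0.0431 falls to 0.0333, ratio 0.771, a 23% cut.

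The 23% needs no true individual change at all over 18 weeks, and I do not rely on it. Equal correlations also make Week 18 as close to Day 0 as Screening is, so the upper part of the 7 to 20% range is optimistic. At sd = 0.3 the cut is 7 to 11%.

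**Correlations that differ.** Ratios are to Day 0 only.

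| rb / r1 / r2 | Mean of two | Both as covariates |
|---|---|---|
| 0.8 / 0.7 / 0.70 | 0.893 | 0.893 |
| 0.8 / 0.7 / 0.65 | 0.968 | 0.956 |
| 0.8 / 0.7 / 0.60 | 1.040 | 0.991 |
| 0.7 / 0.7 / 0.55 | 1.060 | 0.986 |
| 0.8 / 0.6 / 0.50 | 1.037 | 0.998 |

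The mean breaks even at r2/r1 = √[2(1 + rb)] − 1, which is 0.84 at rb = 0.7 and 0.90 at rb = 0.8. Below that it is worse than the SAP rule. Two covariates never raise the residual variance.

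**Degree of freedom.** With 3 × 35 = 105 subjects, residual degrees of freedom fall from 101 to 100, a cost of about 1% (101/100 = 1.01). That offsets the gain in the weakest rows.

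**The case against.** The strongest case for leaving the SAP alone is that it follows the Protocol's own Baseline. A table footnote applies Screening results as Baseline only for HbA1c and the MRI measures, while chemistry and lipids have a separate Day 0 draw. The last pre-dose value is a conventional choice, and ANCOVA on it is valid under randomisation. The two draws are also not pure replicates. Screening AST and ALT are checked against eligibility limits, prohibited medicines are to be stopped between the visits, and up to 28 days may separate them. The variance-component figures are on the log scale, whereas the SAP plans untransformed changes.

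Most of this stands. It is why the gain is given as a range, and why a second covariate is preferable to redefining Baseline. Selection at Screening shifts the mean change within every arm but does not bias the randomised comparison. The correlation formulae do not depend on the log scale. What remains is that an available predictor goes unused without a stated reason.

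Two stronger readings are tempting, and the documents do not support them:

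- **That the SAP contradicts Table 8.** The Table 8 average belongs to a safety-monitoring algorithm, and the SAP definition is expressly for analysis. The two may differ.
- **That a single reading materially distorts ALT normalisation.** Under assumed values (median ALT 45, ULN 41, sb 0.45, sw 0.20, no drug effect), 15.9% normalise by chance with one reading and 14.7% with the mean of two. That is about one percentage point, alike in every arm.

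**Conclusion.** The point holds as a cheap improvement. The SAP's rule is valid and unbiased, but it gives up some precision on seven secondary analytes. The loss is about 7 to 20% of residual variance if Screening and Day 0 predict Week 18 about equally well. If Screening predicts less well, it falls to about 1 to 4%, and in the weakest case tried to nothing once the degree of freedom is counted. Which case applies cannot be settled from the documents.

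A reader might infer that the primary result is weakened because Baseline ALT is a covariate in the liver-fat model. Any such effect is likely to be minor: liver fat has one pre-dose value by design, its own Baseline is in the model, and the sample size does not change. What the SAP lacks on ALT is an explicit statement of which Baseline applies where.

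**What to change.** Before unblinding, amend the SAP as follows.

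1. **SAP 5.2.5.** For ALT, AST, GGT, fasting glucose, LDL-c, HDL-c and triglycerides, keep Day 0 as the reference for change and as a covariate, and add the Screening value as a second covariate. Use the most recent Screening value if the test was repeated or the subject was re-screened. If only one pre-dose value exists, enter it in both places.
2. **SAP 3.3.4.** Add the Screening value to the imputation model for these analytes, so that it contains every covariate of the analysis model.
3. **SAP 3.3.7.** State that the Table 8 average applies to liver monitoring, and name the Baseline ALT used as the liver-fat covariate and for the elevated-ALT subset.

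The mean of the two values is an acceptable alternative, but it can lose about 4 to 6% in variance if Screening predicts Week 18 clearly less well than Day 0.

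The cost is one degree of freedom, the missing-value rule and a few lines of SAP text and programming. No new data or visits are needed, and the Table 8 rule is untouched.
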